7.4.2.19 ENDOCRINE DISORDERS

Treatment-emergent elevation of thyroid-stimulating hormone (TSH) has been observed with cabozantinib treatment. Currently available data are insufficient to determine the mechanism of thyroid function test alterations and its clinical relevance. Management of thyroid dysfunction (e.g., symptomatic hypothyroidism) should follow accepted clinical practice guidelines.

7.4.2.20 ANGIOEDEMA

Angioedema should be managed according to standard practice. The subject should be observed until symptoms resolve, with particular attention to maintaining an open airway.

8 CONCOMITANT THERAPY

8.1 ALLOWED, PROHIBITED AND RESTRICTED THERAPIES

Allowed Therapy

- Antiemetics and antidiarrheal medications are allowed prophylactically according to standard clinical practice if clinically indicated.
- Granulocyte colony-stimulating factors (G-CSF or GM-CSF) are allowed if used per clinical guidelines (e.g., ASCO or ESMO guidelines).
- Bisphosphonates can be used to control bone loss or hypocalcemia if the benefit outweighs the risk per the investigator's discretion.

Note: osteonecrosis of the jaw has been reported in subjects using bisphosphonates (Section 7.4.2.9). Oral examinations are recommended at screening to determine eligibility and periodically during the study. In addition, subjects should be advised regarding oral hygiene practice and to quickly report symptoms to the investigator. Frequent monitoring for potentially overlapping toxicities with study treatment is recommended.

- Transfusions and hormone replacement should be utilized as indicated by standard clinical practice.
- Individualized anticoagulation therapy with heparin is allowed if it can be provided safely and effectively under the following circumstances:
 - *Therapeutic doses of LMWH after first dose of study treatment* are allowed if clinically indicated (e.g., for the treatment of deep venous thrombosis), and the benefit outweighs the risk per the investigator's discretion. For management of thromboembolic complications while on study, refer to Section 7.4.2.5.
 - Accepted clinical guidelines regarding appropriate management while receiving anticoagulation therapy with heparins must be followed. This includes, but is not limited to, subject education regarding potential adverse drug reactions, monitoring laboratory parameters, dose adjustments (e.g., due to kidney dysfunction).
 - For restrictions on oral anticoagulants see below.

Potential drug interactions with cabozantinib are summarized in Section 8.2.

Prohibited or Restricted Therapy

The following therapies are prohibited during the 28 day treatment with cabozantinib on ARM A:

- Any investigational agent or investigational medical device.
- Oral anticoagulants (e.g., warfarin or other coumarin-related agents, direct thrombin or direct FXa inhibitors, or antiplatelet agents such as clopidogrel, or chronic use of aspirin above low dose levels for cardioprotection per local applicable guidelines).

- Any nonprotocol systemic anticancer treatment (e.g., chemotherapy, immunotherapy, radionuclides, drugs or herbal products used specifically for the treatment of the cancer under investigation).

The following therapies should be avoided during the 28 day treatment with cabozantinib on ARM A.

- Please review medications taken by the subject with your pharmacist/physician as this is not an all inclusive list of medications that may interact with cabozantinib.
- Erythropoietic stimulating agents (e.g., epoetin alfa and darbepoetin alfa) should not be used based on a report of increased risk of tumor recurrence/progression associated with erythropoietin (Wright et al 2007).
- Concomitant medications that are known to prolong the QTc interval should be avoided in subjects who receive cabozantinib until they have permanently discontinued cabozantinib treatment (refer to <http://www.qtdrugs.org> for a list of drugs which have the potential to prolong the QTc interval).
- Chronic co-administration of cabozantinib with strong inducers of the CYP3A4 family (e.g., phenytoin, carbamazepine, rifampin, rifabutin, rifapentine, phenobarbital, and St. John's Wort) may significantly decrease cabozantinib concentrations and should be avoided. Selection of alternate concomitant medications with no or minimal CYP3A4 enzyme induction potential is recommended.
- Caution must be used when discontinuing treatment with a strong CYP3A4 inducer in a subject who has been concurrently receiving a stable dose of cabozantinib, as this could significantly increase the exposure to cabozantinib.
- Co-administration of cabozantinib with strong inhibitors of the CYP3A4 family (e.g., boceprevir, conivaptan, posaconazole, ketoconazole, itraconazole, clarithromycin, atazanavir, indinavir, nefazodone, nelfinavir, saquinavir, ritonavir, lopinavir, telaprevir, telithromycin, and voriconazole) may increase cabozantinib concentrations and should be avoided. Grapefruit, star fruit, and Seville oranges may also increase plasma concentrations of cabozantinib and should be avoided.

Additional information on potential drug interactions with cabozantinib is provided in Section 8.2.

8.2 POTENTIAL DRUG INTERACTIONS WITH CABOZANTINIB

Cytochrome P450: Data from a clinical drug interaction study (Study XL184-008) show that clinically relevant steady-state concentrations of cabozantinib appear to have no marked effect on the area under the plasma concentration-vs-time curve (AUC) of co-administered rosiglitazone, a CYP2C8 substrate. Therefore, cabozantinib is not anticipated to markedly inhibit CYP2C8 in the clinic, and by inference, is not anticipated to markedly inhibit other CYP450 isozymes that have lower [I]/K_i values compared to CYP2C8 (i.e., CYP2C9, CYP2C19, CYP2D6, CYP1A2, and CYP3A4). In vitro data indicate that cabozantinib is unlikely to induce cytochrome P450 enzymes, except for possible induction of CYP1A1 at high cabozantinib concentrations (30 μM).

Cabozantinib is a CYP3A4 substrate and a weak substrate for CYP2C9 (but not a CYP2D6, CYP2C8, CYP2C19, CYP2B6, or CYP1A2 substrate), based on data from in vitro studies. Results from a clinical

pharmacology study, XL184-006, showed that concurrent administration of cabozantinib with the strong CYP3A4 inducer, rifampin, resulted in an approximately 77% reduction in cabozantinib exposure (AUC values) after a single dose of cabozantinib in healthy volunteers. Chronic co-administration of cabozantinib with strong inducers of the CYP3A4 family (e.g., phenytoin, carbamazepine, rifampin, rifabutin, rifapentine, phenobarbital, and St. John's Wort) may significantly decrease cabozantinib concentrations. The chronic use of strong CYP3A4 inducers should be avoided. Other drugs that induce CYP3A4 should be used with caution because these drugs have the potential to decrease exposure (AUC) to cabozantinib. Selection of alternate concomitant medications with no or minimal CYP3A4 enzyme induction potential is recommended.

Results from a clinical pharmacology study, XL184-007, showed that concurrent administration of cabozantinib with the strong CYP3A4 inhibitor, ketoconazole, resulted in a 38% increase in the cabozantinib exposure (AUC values) after a single dose of cabozantinib in healthy volunteers. Co-administration of cabozantinib with strong inhibitors of the CYP3A4 family (e.g., boceprevir, conivaptan, posaconazole, ketoconazole, itraconazole, clarithromycin, atazanavir, indinavir, nefazodone, nelfinavir, saquinavir, ritonavir, lopinavir, telaprevir, telithromycin, and voriconazole) may increase cabozantinib concentrations. Grapefruit, star fruit and Seville oranges may also increase plasma concentrations of cabozantinib and should be avoided. Strong CYP3A4 inhibitors should be avoided and other drugs that inhibit CYP3A4 should be used with caution because these drugs have the potential to increase exposure (AUC) to cabozantinib. Selection of alternate concomitant medications with no or minimal CYP3A4 enzyme inhibition potential is recommended.

Please refer to the drug interaction tables at the following websites for lists of substrates, inducers, and inhibitors of selected CYP450 isozyme pathways:

<http://medicine.iupui.edu/clinpharm/ddis/table.aspx>

<http://www.fda.gov/Drugs/DevelopmentApprovalProcess/DevelopmentResources/DrugInteractionsLabeling/ucm080499.htm>

Protein Binding: Cabozantinib is highly bound ($\geq 99.7\%$) to human plasma proteins. Therefore, highly protein bound drugs should be used with caution with cabozantinib because there is a potential displacement interaction that could increase free concentrations of cabozantinib and/or a co-administered highly protein-bound drug (and a corresponding increase in pharmacologic effect).

Other Interactions: Food may increase exposure levels of cabozantinib by 57%, fasting recommendations should be followed. In vitro data suggest that cabozantinib is unlikely to be a substrate for P-glycoprotein, but it does appear to have the potential to inhibit the P-glycoprotein transport activity. Therefore, cabozantinib may have the potential to increase plasma concentrations of co-administered substrates of P-glycoprotein. Additional details related to these overall conclusions can be found in the investigator brochure.

Administration of the proton pump inhibitor (PPI) esomeprazole resulted in no clinically-relevant effect on cabozantinib plasma PK in healthy volunteers. Therefore, concomitant use of gastric pH modifying agents (i.e., PPIs, H₂ receptor antagonists, and antacids) is not contraindicated in subjects administered cabozantinib.

Additional details regarding potential drug interactions with cabozantinib can be found in the investigator brochure.

Cabozantinib was shown to be a substrate of drug transporter MRP2 in an in vitro assay. Administration of MRP2 inhibitors to subjects may result in increases in cabozantinib plasma concentrations.

8.3 STUDY TREATMENT ACCOUNTABILITY

The investigator or designee will maintain accurate records of receipt of all study treatment including dates of receipt. In addition, accurate records will be kept regarding the date, lot number, and how much study treatment is dispensed and used by each subject in the study. Reasons for deviation from the expected dispensing regimen must also be recorded. At completion of the study, to satisfy regulatory requirements regarding drug accountability, all unused study treatment will be reconciled and destroyed according to applicable state, federal, and local regulations.

9 STUDY INTERVENTION DISCONTINUATION AND PARTICIPANT DISCONTINUATION/WITHDRAWAL

9.1 DISCONTINUATION OF STUDY INTERVENTION

At any time, the study may be terminated by the study sponsor, the sponsoring institution, or by Exelixis. Should this be necessary, Exelixis and the investigator will arrange the procedures on an individual study basis after review and consultation. In terminating the study, Exelixis and the investigator will ensure that adequate consideration is given to the protection of the subjects' interests. Upon study termination, the investigator(s) shall cease enrolling subjects into the study, and shall discontinue conduct of the study as soon as is medically practicable.

10 SAFETY

10.1 ADVERSE EVENTS AND LABORATORY ABNORMALITIES

10.1.1 ADVERSE EVENTS (AES)

An AE is any untoward medical occurrence in a patient or clinical trial subject administered a medicinal product and which does not necessarily have a causal relationship with this treatment. An adverse event can therefore be any unfavorable and unintended sign (e.g. an abnormal laboratory finding), symptom, or disease temporarily associated with the use of a medicinal product, whether or not considered related to the medicinal product. An adverse event can arise from any use of the drug (e.g. off-label use, use in combination with another drug) and with any route of administration, formulation, or dose,

including an overdose. This definition also includes AEs associated with medication errors and uses of the investigational product outside what is in the protocol, including misuse and abuse. Pre-existing medical conditions that worsen during the study should be recorded as AEs. Abnormal laboratory values, ECG findings, or vital signs are to be recorded as AEs if they meet the criteria described in this protocol. All untoward events that occur from the first dose of study drug through 30 days after the decision to discontinue study treatment (or the date the subject is deemed to be a screen failure) are to be recorded by the investigational site. This requirement includes AEs from unscheduled as well as scheduled visits and includes the new onset of or increase in pain during this period.

Adverse event terms recorded on the CRFs will be mapped to preferred terms using the Medical Dictionary for Regulatory Activities (MedDRA). Seriousness, severity grade, and relationship to study treatment will be assessed by the investigator. Severity grade will be defined by the current version of the National Cancer Institute (NCI)-Common Terminology Criteria for Adverse Events (CTCAE).

10.1.2 SERIOUS ADVERSE EVENTS (SAES)

The SAE definition and reporting requirements are in accordance with the International Conference of Harmonisation (ICH) Guideline for Clinical Safety Data Management: Definitions and Standards for Expedited Reporting, Topic E2A.

An SAE is defined as any untoward medical occurrence that at any dose:

- Result in death;
- Is life-threatening (i.e., in the opinion of the investigator, the AE places the subject at risk of death; it does not include an event that, had it occurred in a more severe form, might have caused death);
- Requires inpatient hospitalization or results in prolongation of an existing hospitalization;
 - Note: While most hospitalizations necessitate reporting of an SAE, some hospitalizations do not require SAE reporting, as follows: elective or previously scheduled surgeries or procedures for pre-existing conditions that have not worsened after initiation of treatment (e.g., a previously scheduled ventral hernia repair); pre-specified study hospitalizations for observation; or events that result in hospital stays of fewer than 24 hours and that do not require admission (e.g., an ER visit for hematuria that results in a diagnosis of cystitis and discharge home on oral antibiotics). SAEs must, however, be reported for any surgical complication resulting in prolongation of the hospitalization.
- Results in persistent or significant disability or incapacity:
 - Note: The term “disability” refers to events that result in a substantial disruption of a subject’s ability to conduct normal life function.

- Is a congenital anomaly or birth defect;
- Is an important medical event (IME):
 - Note: The term “important medical event” refers to an event that, based upon appropriate medical judgment, may not be immediately life-threatening or result in death or hospitalization, but may jeopardize the subject or require intervention to prevent one of the other serious outcomes listed. Examples of IMEs include intensive treatment in an emergency room or at home for allergic bronchospasm; blood dyscrasias, or convulsions that do not result in hospitalization; or development of product dependency or product abuse.

10.1.3 RELATIONSHIP TO STUDY TREATMENT

Assessment of the relationship of the AE to the study treatment by the investigator is based on the following two definitions:

- Not Related: A not-related AE is defined as an AE that is not associated with the study treatment and is attributable to another cause or there is no evidence to support a causal relationship;
- Related: A related AE is defined as an AE where a causal relationship between the event and the study treatment is a reasonable possibility. A reasonable causal relationship is meant to convey that there are facts (e.g., evidence such as dechallenge/rechallenge) or other clinical arguments to suggest a causal relationship between the AE and study treatment. Possibly and probably related AEs should be documented as related.

10.1.4 SERIOUS ADVERSE EVENT REPORTING

As soon as an investigator becomes aware of an AE that meets the definition of ‘serious,’ this must be documented on an SAE Report Form and include the following: (i) all SAEs that occur after starting cabozantinib and through 30 days after the decision to discontinue study treatment and (ii) any SAEs assessed as related to study treatment or study procedures (for patients on the cabozantinib arm), from the time of informed consent, even if the SAE occurs more than 30 days after the decision to discontinue study treatment. The prostatectomy is considered a standard of care procedure, not a study procedure. SAEs solely related to the prostatectomy will not be collected.

All SAEs that are assessed by the PI as **related** to drug or study procedure and all pregnancy/lactation reports regardless of outcome must be sent to the Duke Safety Desk within one (1) business day of the PI’s knowledge of the event. The Duke Safety Desk will report to Exelixis within one (1) business day of the receipt of the report. The reports must be sent to [contact] or [contact].

- The PI will perform adequate due diligence with regard to obtaining follow-up information on incomplete reports. All follow-up information must be sent to Exelixis within one (1) business

day of the PI's receipt of the new information. Upon Exelixis request, the PI will query for follow-up information.

10.1.5 REGULATORY REPORTING

The Investigator will assess the expectedness of each related SAE. The current cabozantinib Reference Safety Information (Appendix K of the most recent approved Investigator Brochure) will be used as the reference document for assessing the expectedness of the event with regard to cabozantinib. All serious unexpected adverse drug reactions (unexpected related SAEs) must be reported to all appropriate regulatory authorities and Ethics Committees by the investigator as required by 21 CFR 312.32 or by Directive 2011/20/EC:

- These reports are to be filed utilizing the Form FDA 3500A (MedWatch Form) or a CIOMS-1 form;
- Exelixis reserves the right to upgrade the Investigator assessment of an SAE based on Exelixis assessment.
- Institutions and PIs shall promptly provide all information requested by Exelixis regarding all adverse events occurring during the conduct of the study.
- The PI is responsible for complying with all regulatory authority reporting requirements for the study that are applicable to the sponsor of a clinical trial. The PI shall provide a copy of all responses to regulatory agency requests, periodic reports, and final study reports to Exelixis within one (1) business day of the submission.
- Exelixis will provide relevant product safety updates and notifications, as necessary. In the case of multi-center studies, it is the responsibility of the sponsoring PI/Institution to disseminate these updates to participating PIs.

10.2 OTHER SAFETY CONSIDERATIONS

10.2.1 LABORATORY DATA

All laboratory data required by this protocol and any other clinical investigations should be reviewed. Any abnormal value that leads to a change in subject management (e.g., dose reduction or delay or requirement for additional medication or monitoring) or that is considered to be of clinical significance by the investigator should be reported as an AE or SAE as appropriate.

10.2.2 PREGNANCY/LACTATION EXPOSURE

Pregnancy in partner, although not an SAE, should be reported to Exelixis. The partner will be asked to sign a pregnant partner form allowing collection of her information and the offspring. The outcome of a pregnancy (for the partner of a subject) and the medical condition of any resultant offspring must be reported to Exelixis, if the pregnant partner agrees. Any birth defect or congenital anomaly must be

reported as an SAE, and any other untoward events occurring during the pregnancy must be reported as AEs or SAEs, as appropriate.

10.2.3 MEDICATION ERRORS/OVERDOSE

Any overdose, or study drug administration error that results in an AE, even if it does not meet the definition of serious, requires reporting within one (1) business day to Exelixis.

10.2.4 FOLLOW-UP OF ADVERSE EVENTS

Any related SAEs or any AEs assessed as related that led to treatment discontinuation, including clinically significant abnormal laboratory values that meet these criteria, ongoing 30 days after the decision to discontinue study treatment must be followed until either resolution of the event or determination by the investigator that the event has become stable or irreversible. This follow-up guidance also applies to related SAEs that occur more than 30 days after the decision to discontinue study treatment. The status of all other continuing AEs will be documented as of 30 days after the decision to discontinue study treatment.

10.3 SAFETY MONITORING

Safety data will be monitored by the PI, urology co-PI and statistician by regular reviews. This monitoring is separate, but complementary to the stopping rules.

A safety assessment will at the following time points:

- The first 6 subjects receiving cabozantinib treatment have completed the day 57-85 safety visit.
- The first 12 subjects receiving cabozantinib treatment have completed the day 57-85 safety visit.
- The first 18 subjects receiving cabozantinib treatment have completed the day 57-85 safety visit.

The statistician or their designee will compile a report of all AEs documented on study, including any SAEs and DLTs. The PI and urology co-PI will review the report and determine if the safety data warrant a change to the study. Enrollment will not be suspended for the safety assessments.

11 STATISTICAL CONSIDERATIONS

11.1 STATISTICAL METHODS

Safety Lead-In and Stopping Rules. The first 6 subjects assigned to cabozantinib treatment will constitute the *Safety Lead-In cohort*, which will be only accrued at Duke. Of these 6 subjects receiving cabozantinib, the first 3 subjects will be enrolled sequentially (after each prior subject completes the day 57-85 safety visit). After this, the remaining 3 subjects receiving cabozantinib may be enrolled non-sequentially in the cohort. If there are ≥ 2 dose-limiting toxicities (DLTs) in the first 6 subjects, the trial will be stopped for safety purposes (*first stopping rule*). DLTs are defined as CTCAE v5 grade ≥ 2 wound dehiscence or wound complication, any grade fistula, grade ≥ 2 hemorrhage of any type, grade ≥ 3 infections [except urinary tract infections (UTIs) which are expected in this population], any AE that leads to permanent discontinuation of cabozantinib, or other grade ≥ 3 cabozantinib-related

perioperative complications. The DLT period is defined as day 1 of drug through day 57 of the protocol (inclusive). The seventh subject randomized to cabozantinib may not be enrolled until the sixth subject completes the day 57-85 safety visit and the Duke principal investigator agrees that the stopping rule should not be put into effect. From the seventh subject on, subjects may be accrued at ex-Duke site(s). A *second stopping rule* will be triggered if there are ≥ 3 DLTs in the first 12 subjects treated with cabozantinib. In the event that a stopping rule is triggered, thorough review of the cabozantinib-treated patients' files will be performed and the Duke principal investigator will consider whether the trial can be redesigned or should be permanently discontinued.

Sample Size Justification. The primary endpoint of this randomized phase II study is the apoptotic index by cleaved caspase-3 in prostatectomy specimens following 4 weeks of treatment with cabozantinib compared with prostatectomy specimens of untreated patients. The target sample size of convenience is 30 patients where the randomization allocation ratio will be 2:1 cabozantinib-to-control. The randomization will not be stratified on any variable. The null hypothesis is that the mean apoptotic indices are equal between the two groups. The percent of tumor cells positive for cleaved caspase 3 staining for each patient will be evaluated for the primary objective. The 6 subjects assigned during the Safety Lead-In Cohort are included in the 30 patient sample size and 2:1 randomization allocation ratio.

Based on data from a prior, unpublished pre-prostatectomy study of sunitinib, we expect the controls to have minimal staining (i.e., $\leq 5\%$). In the proposed study we will enroll 10 controls and 20 cabozantinib-treated patients to demonstrate increased staining (i.e., $>5\%$). A two sample t-test will be used to compare group means. With 10 and 20 evaluable patients in the control and cabozantinib-treated groups, respectively, the test will provide 70% power to detect a mean (for positive tumor cells percentage) difference of one-fold standard deviation based on a two-sided type I error of 0.05; or 96% power to detect an one-and-half fold standard deviation difference. Assuming a 10% unevaluable rate, we will enroll up to 33 patients total to have 30 evaluable patients.

Data Analysis. Box plots and statistical summaries of apoptotic (cleaved caspase-3, TUNEL), proliferation (Ki-67), and MVD (CD31) indices will be presented. In addition, the t-test will be used to compare the two arms on apoptotic index, proliferation and MVD indices. Further, the Chi-square test will be used to compare the two treatment arms on pathologic complete response rate (pCR) and pathologic T2 (pT2) rate. The angiome, gene expression, cell-free DNA and mesenchymal markers analyses will be reported descriptively as the trial's limited sample size will not permit definitive analyses for these exploratory objectives. The t-test will be used to compare the two arms' serum and tissue androgen and androgen precursor levels.

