Exploratory Objectives:	
 1. To estimate the pathologic complete response rate (pCR) and \leqpathologic T2 (\leqpT2) rate in each arm. 2. To evaluate relapse-free survival in each arm. 3. To compare apoptosis (TUNEL), proliferation (Ki-67), and microvessel density (CD31) indices in prostatectomy specimens from patients who undergo immediate prostatectomy versus those treated with cabozantinib prior to prostatectomy. 4. To measure expression levels of c-MET, VEGF, and HGF, as well as activation status of c-MET in prostate tissue. 5. To describe changes in plasticity signaling markers associated with prostate tumors, including vimentin, AR, SNAIL, AXL, and N-cadherin with cabozantinib exposure. 6. To evaluate PTEN and p53 genomic and protein expression status in tumor tissue 7. To demonstrate that cabozantinib is safe and tolerable in patients undergoing radical prostatectomy. 8. To demonstrate that surgery is safe and feasible in patients undergoing treatment with cabozantinib. 9. To collect plasma angiome samples (multiplex ELISA) for analysis and correlation with primary and key secondary endpoints. 10. To describe gene expression patterns (in particular those associated with apoptosis, androgen receptor signaling, c-MET activation, and a c-MET-specific endocytosis panel) correlated with cabozantinib administration using RNA sequencing.

	
 11. To explore changes in serum and intratumoral androgen concentrations related to cabozantinib treatment. 12. To collect cell-free DNA (cfDNA) for analysis and correlation with primary and key secondary endpoints.

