2.3 HYPOTHESES

We hypothesize that in those treated with cabozantinib followed by prostatectomy compared with immediate prostatectomy:

1. Apoptotic index (cleaved caspase-3) will be 2-fold higher in prostate cancer tissues following cabozantinib as compared with men proceeding to immediate radical prostatectomy.
2. Infiltration of neutrophils and release of neutrophil chemotactic factors (CXCL12 and HMGB1) will be 2-fold higher in prostate cancer tissues following cabozantinib as compared with men proceeding to immediate radical prostatectomy.

3. Interleukin-1 receptor antagonist will be upregulated and MDSC-promoting cytokines will be suppressed in prostate cancer tissues following cabozantinib as compared with men proceeding to immediate radical prostatectomy.
4. The M1 macrophage population will be decreased without affecting the M2 macrophage population in prostate cancer tissues following cabozantinib as compared with men proceeding to immediate radical prostatectomy.
5. Pathologic complete responses (pCRs) will be observed in the minority population of men harboring the TP53 mutant / PTEN null localized prostate cancer and will be associated with myeloid immune cell activation in the prostate and peripheral blood.

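### The objective is to estimate the pCR and ≤pT2 rates in each arm, but section 11.1 plans only a chi-square comparison at 20 v 10 and no confidence interval

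*Combined protocol and SAP*

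**What the plan says.** Exploratory objective 1 (Synopsis 1.1 and the table in section 3) opens with "To estimate the pathologic complete response rate (pCR". It adds the ≤pT2 rate and asks for both in each arm. The aim is therefore estimation, arm by arm.

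The Data Analysis paragraph of section 11.1 gives the only planned analysis of these rates: "the Chi-square test will be used to compare the two treatment arms on pathologic complete response rate (pCR) and pathologic T2 (pT2) rate". It names no continuity correction, exact test, sparse-table rule or interval. The only confidence interval anywhere in the documents is a hazard ratio cited from an earlier trial in section 2.2.

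The group sizes are in the sample size paragraph: "With 10 and 20 evaluable patients in the control and cabozantinib-treated groups, respectively". No pCR rate is assumed anywhere. Hypothesis 5 in section 2.3 says only that "Pathologic complete responses (pCRs) will be observed in the minority population of men" with a particular TP53/PTEN status.

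The same Data Analysis paragraph gives the small sample as its reason for only describing the mesenchymal-marker, cfDNA, angiome and gene-expression results. It does not extend that reasoning to pCR or pT2.

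**The concern.** The planned analysis does not answer the stated question. A chi-square p-value says nothing about how high or low each arm's rate could be, and with 20 and 10 men that uncertainty is the main thing a reader needs.

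The chosen test is also a poor fit for pCR. The event is expected in few men, so expected counts will be small and the large-sample approximation rough. Because the version of the test is not named, two analysts following 11.1 could report different p-values from the same table. If there is no pCR at all, the named test gives no result.

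At stake is the clarity of one exploratory result. The primary comparison of cleaved caspase-3 is not affected.

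**Working it through.** **Inputs.** 20 treated and 10 control evaluable men (11.1). The two-sided 0.05 level is stated for the primary t-test only and is assumed here for the rate comparisons. The event rates below are assumptions, because the documents give none.

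**The plan's own figures.** No power or precision is given for pCR or pT2. The only power figures are for the t-test: "the test will provide 70% power to detect a mean (for positive tumor cells percentage) difference of one-fold standard deviation", "or 96% power to detect an one-and-half fold standard deviation difference". With 28 degrees of freedom the noncentrality is d/√(1/10 + 1/20), which is 2.58 for d = 1 and 3.87 for d = 1.5. Power is then 70.3% and 96.2%. The stated 70% and 96% reproduce, which confirms the 20 v 10 reading.

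**Expected counts.** With T events in 30 men, the expected number in controls is 10T/30 = T/3. Three pCRs in the whole trial give an expected 1 in controls.

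**No events.** If T = 0 the Pearson statistic is 0/0. The probability is (1 − p)^30 for a common rate p:
- p = 5%: 0.95^30 = 0.215
- p = 2%: 0.98^30 = 0.545

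**One table, three p-values.** Take 7/20 v 0/10, with cells 7, 13, 0 and 10.
- Uncorrected Pearson: 30 × (7×10 − 13×0)² / (20 × 10 × 7 × 23) = 147,000/32,200 = 4.57, p = 0.033
- Continuity-corrected: 30 × (70 − 15)² / 32,200 = 90,750/32,200 = 2.82, p = 0.093
- Fisher: with 7 events fixed, the probability of 7, 2, 1 or 0 falling in the treated arm is 0.0381 + 0.0235 + 0.0021 + 0.0001 = 0.064

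This is the smallest treated-only count that uncorrected Pearson calls significant; 6/20 v 0/10 gives 0.053. The issue is not confined to rare events: 12/20 v 2/10, a possible ≤pT2 result, gives 0.038 uncorrected and 0.058 by Fisher.

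**All 21 × 11 = 231 tables.**
- Uncorrected Pearson and Fisher disagree at 0.05 in 12 tables, each time with Pearson significant and Fisher not.
- Continuity-corrected chi-square and Fisher disagree in 10 tables, each time with Fisher significant and chi-square not.

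**Type I error, maximum over common rates.** Uncorrected Pearson 5.2%, Fisher 3.3%.

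**Power at assumed rates of 20% v 0%.** With no control events, uncorrected Pearson needs at least 7 treated events and Fisher at least 8. For a binomial with n = 20 and p = 0.2, the probabilities are 8.7% and 3.2%.

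**What intervals would show.** For 0/n the exact upper 95% limit is 1 − 0.025^(1/n).

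| Result | Exact 95% interval |
|---|---|
| 0/20 | 0 to 16.8% |
| 2/20 | 1.2 to 31.7% |
| 10/20 | 27.2 to 72.8% |
| 0/10 | 0 to 30.8% |
| 5/10 | 18.7 to 81.3% |

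**The case against.** The strongest reply is that nothing depends on this. The endpoints are exploratory, section 2.2 presents the study as hypothesis-generating, and no stopping rule, alpha or go/no-go decision attaches to pCR or ≤pT2. With no pCRs the team would simply report 0/20 and 0/10. All of that stands and keeps the point small. It does not supply the missing intervals: a bare 0/20 does not tell the reader that a true rate near 17% is still compatible with the data.

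A second reply is that chi-square controls its error here. It does. A reader might infer from the small expected counts that the test is invalid or yields excess false positives, but a maximum of 5.2% does not support that. The usual rule that every expected count should reach 5 is a convention and appears nowhere in the documents. Under a looser rule of at least 1, any total from 3 to 27 events passes. The 12 discordant tables are also a raw count: at common rates from 1% to 50%, the 0.05 verdict changes in about 0.3% to 2.7% of trials.

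A reader might further infer that chi-square always leans towards significance, or that it would produce findings against cabozantinib. Neither follows. The first holds only for the uncorrected version, and 11.1 does not say which version is meant. The second needs pCRs in untreated men, for which the documents give no expectation; hypothesis 5 concerns men treated with cabozantinib. The 7/20 v 0/10 table is itself a rejection in favour of the drug. Any asymmetry comes from 2:1 allocation with rare events, and Fisher's test shares it.

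Finally, Fisher's test is conservative and loses power that is already low. That is a real cost, so the intervals are the essential part of the change.

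**Conclusion.** The point holds as a mismatch between objective and analysis, with a test poorly suited to sparse tables. The missing intervals follow from reading the objective beside 11.1 and need no statistical convention. The test-dependent p-values are exact for 20 v 10 at an assumed 0.05 level. The 21% and 55% chances of no pCR rest on assumed rates of 5% and 2% in both arms. Because type I error is controlled and the endpoints are exploratory, this is a low-cost improvement. The documents do not support reading it as a flaw in the primary analysis or in the trial's conclusions.

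**What to change.** In the Data Analysis paragraph of 11.1, replace the chi-square sentence with:

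> The pCR and ≤pT2 rates will be reported per arm with exact (Clopper-Pearson) 95% CIs; any between-arm comparison will use Fisher's exact test and be treated as exploratory.

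This also aligns the wording, since 11.1 writes pT2 where the objective and endpoint say ≤pT2. The cost is one sentence, with no change to sample size, conduct or data collection. The downside is Fisher's conservatism (power 3.2% against 8.7% for 20% v 0%), which matters little if the intervals carry the result.
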